10.2.2.2 Participants for sensitivity analyses, per type of SLE SOC (biologics and nonbiologics)

For the primary outcomes (objectives 1 to 4), sensitivity analyses will be performed to compare patients exposed to anifrolumab with two groups of patients exposed to SLE SOC: patients exposed to SLE SOC biologics and patients exposed to SLE SOC non-biologics. Additional sub-cohorts will be re-assessed from the *overall source population* (obtained in step 1, Section 10.2.2.1). Patients initiating anifrolumab will be matched with comparable patients not exposed to anifrolumab but exposed to SLE SOC biologic drugs (belimumab or rituximab, including biosimilars) and with those exposed to SLE SOC non-biologics.

Subgroup cohorts (for malignancy and serious infection outcomes) (Table 5) will consider the same inclusion and exclusion criteria described for the main analyses (Section 10.2.2.1) from step

2 until step 4. However, at step 2 (for exposed to anifrolumab) and at step 4 (for unexposed to anifrolumab) the following additional criteria will be applied:

- Exposed patients: exclusion of patients with a prescription of SLE SOC biologics (belimumab or rituximab) in the previous 12 months.
- Unexposed to anifolumab patients, exposed to SLE SOC biologics: inclusion of patients with a prescription of SLE SOC biologics in the previous 12 months regardless of other SLE SOC).
- Unexposed to anifolumab patients, exposed to SLE SOC non-biologics: inclusion of patients with a prescription of SLE SOC and exclusion of those with a prescription of SLE SOC biologics in the previous 12 months.

			Additional criteria to	
	Input	Exposed and unexposed	be applied at STEP 2	Sub-cohorts created at
Outcome	population	units	to the input	STEP 4
			population	
Malignancies	Overall	Exposed to anifrolumab	EXCLUSION:	malign_sub_exp
	source		Patients exposed to SLE	
	population		SOC biologics in the	
		I I a serve a set da ser i fa share sh	previous 12 months	
		Unexposed to anifrolumab	INCLUSION: Patients with SLE SOC	malign_sub_unexp_bio
		(exposed to SLE SOC		
		biologics)	including a biologic	
			drug in the previous 12	
			months	
		Unexposed to anifrolumab	EXCLUSION:	malign_sub_unexp_nonbio
		exposed to SLE SOC non-	Patients exposed to SLE	
		biologics	SOC biologics in the	
			previous 12 months	
Serious	Overall	Exposed to anifrolumab	EXCLUSION:	inf_sub_exp
Infections	source		Patients exposed to SLE	
	population		SOC biologics in the	
			previous 12 months	

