10.4 Data sources

A feasibility assessment was conducted between June 2022 and January 2023 to assess the suitability of the proposed data sources to address this study's research question and objectives. Information was collected from the data source holders and supplemented by desktop research. Data sources from eight countries (Denmark, Finland, France, Germany, Spain, Sweden, UK, USA) and five SLE specific registries (SLE Registry Germany, Spanish Society of Rheumatology systemic lupus erythematosus registry [RELESSER], Swedish Rheumatology Quality Register [SRQ], OM1 Lupus Registry from the USA and the Systemic Lupus Erythematosus International Collaborating Clinics [SLICC]) were assessed in the feasibility assessment. Of the eight countries evaluated, four countries were selected: Denmark, France, Germany, and Spain. None of the SLE specific registries evaluated in the feasibility assessment was selected for inclusion in this study. A summary of the rationale for inclusion/exclusion of each data source evaluated in the feasibility assessment is presented in Table 25 of the Appendix 4 Data Sources' details. Data sources were selected based on the ability to capture anifrolumab and SLE SOC use, the study outcomes and the potential size of the study population. The same data sources were assessed for the suitability to examine the research objectives for malignancy and serious infections. The following information was collected for each data source during the feasibility assessment:

- Characteristics of the data source
- Access requirement
- Availability and coding systems of drugs, medical diagnoses, procedures, and laboratory measurements
- Availability and completeness of variables (exposure, outcomes, and covariates)
- Estimated number of SLE diagnosed patients
- Estimate of anifrolumab treated SLE patients in the preceding 12 months (applicable for USA data sources only)

As anifrolumab was approved in 2022 in most European countries, information on the availability of anifrolumab use is limited and unavailable in some data sources. Due to the limited availability of information on anifrolumab exposure data, exposure to biologics indicated for a similar population and with a similar administration route (belimumab IV infusion) was used as a proxy

to evaluate the ability of the data source to capture anifrolumab exposure information when the drug is available in the respective countries.

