10.4.1.2 France: National Health Data System

The French National Health Data System (*Système National des Données de Santé* [SNDS]) is the largest and most comprehensive healthcare dataset available in Europe. It covers 99% of the total French population - around 66 million patients [14]. Individuals enter SNDS at birth or by immigration and exit at death or emigration.

SNDS includes anonymised administrative and healthcare claims data from the French national health care insurance system databases. In particular, data from several databases are available [83]:

• the French National Health Insurance database (*Système national d'information interrégimes de l'Assurance maladie* [SNIIRAM]), available since 2008;

- the French hospital discharge summaries (*Programme de Médicalisation des Systèmes d'Information* [PMSI]), available since 2006;
- the national death registry (*Centre d'épidémiologie sur les causes médicales de Décès* [CépiDC]).

Since 2008, SNIIRAM includes the outpatient reimbursed health expenditures database (*données de consommation interrégimes* [DCIR]), which allows capturing consumption of care.

Reimbursed drugs dispensed through retail pharmacies are available through DCIR and drugs are identified by their ATC code. The date of dispensing, quantity, and brand name are also available. Information on route of administration is available and dose may be estimated from DDD. Information on drug indication is only possible for the inpatient setting, derived from diagnoses.

Hospital administered treatments are available through PMSI, if they are part of the list of highcost drugs (*medicaments listed en sus*). Inclusion in the list allows the reimbursement of drugs, in addition to the hospital episode reimbursement.

Through the PMSI, SNDS includes medical summaries of all hospitalisations from private or public hospitals, including date of stay, medical procedures, devices implanted during the hospital stay, primary diagnosis (main reason for admission) and related diagnosis. These data are encoded according to the ICD-10.

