SNDS contains data on the presence and diagnosis date of long-term chronic disease (LTD). LTD is used together with PMSI to identify patients, namely those with SLE. Patients with LTD are eligible for 100% reimbursement of healthcare expenditure. The request for attribution of LTD is made by the general practitioner and it is not mandatory. Thus, it may be missing, for instance, if the medical expenses are already covered by another chronic disease or the treatment is not expensive. Diagnoses are coded using ICD-10.

SNDS also includes demographic data (including age, sex, place of residence, complementary universal health coverage status (as proxy to socio-economic status), date of death), health encounters, dispensations, medical devices, and laboratory tests (without results) [14].

Data from DCIR and PMSI are annually updated and can be linked for each patient. At the time of the feasibility assessment, data were available until the end of 2021.

Study-specific data

In France, market launch for anifrolumab occurred in April 2022 (Table 3). A favourable reimbursement decision has been made by the health assessment authorities in France. Therefore, it is anticipated that anifrolumab will likely be included in the list of high-cost drugs and thus, will be captured in PMSI.

Data on SLE SOC drugs are available, except for voclosporin and mepacrine, which are not marketed in France. Some drugs, such as methotrexate, mycophenolate mofetil, cyclophosphamide, and cyclosporine are available if the oral forms are used. Chloroquine was in

use until the end of September 2022, when the last product was withdrawn from the market. Furthermore, rituximab and immunoglobulin G – administered as IV at the hospital – are available as they are part of the list of high-cost drugs. Only the pen formulation of belimumab, delivered in retail pharmacies, is captured.

Data on overall and specific malignancies are captured through coded diagnoses at the hospital level. This is also true for serious infections in which diagnoses allow for the identification of specific types of serious infections. Data on prescription/administration of IV antimicrobials are available for inpatients if antimicrobials are part of the list of expensive drugs. Dates of diagnoses (inpatients), hospitalisation, discharge and death are available.

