10.7.1.7 Sensitivity analyses

Sensitivity analyses will be conducted for the primary objectives related to malignancies and/or serious infections.

• For both serious infections and malignancies: Patients exposed to anifrolumab will be compared with two groups of patients exposed to SLE SOC: a) patients exposed to SLE SOC biologics (belimumab and rituximab, including biosimilars) and b) patients exposed to SLE SOC non-biologics.

- For malignancies: As the definition of the latency period is subjective, two other latency periods will be evaluated: no latency period and 24 months latency period.
- For serious infections: A comparative analysis of the incidence for each component of the serious infection definition (i.e., infection leading to hospitalisation, use of intravenous antimicrobials and infection-related death) will be conducted, comparing the incidence among patients exposed to anifrolumab versus comparable moderate/severe SLE patients on SOC. However, as these comparative analyses may be limited by small sample size for each of the components of the serious infections' definition, the analyses will only be conducted if feasible.
- Meta-analysis: The main analysis uses a random effects model to pool the effect estimates across data sources assuming that there is heterogeneity amongst the included data sources (i.e., the true effect is different between the data sources). To assess the robustness of this assumption, the meta-analysis will be conducted with a fixed effects model and its results reported as a sensitivity analysis.

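### In the French data IV belimumab is not recorded, so the biologic/non-biologic sensitivity split puts some IV belimumab users in the wrong group

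*Protocol*

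**What the plan says.** Capture in France is described in Protocol Section 10.4.1.2. The general rule for hospital drugs is "Hospital administered treatments are available through PMSI, if they are part of the list of highcost drugs". For the two standard-of-care biologics, the same section says that "rituximab and immunoglobulin G – administered as IV at the hospital – are available as they are part of the list of high-cost drugs", but for belimumab that "Only the pen formulation of belimumab, delivered in retail pharmacies, is captured". IV rituximab is therefore visible and IV belimumab is not.

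The rule that depends on this capture is in Section 10.2.2.2 and Table 5, and is repeated in Section 10.7.1.7. For the primary outcomes, anifrolumab patients are compared with a biologic and a non-biologic comparator group, biologics being belimumab or rituximab. The anifrolumab arm is subject to "exclusion of patients with a prescription of SLE SOC biologics (belimumab or rituximab) in the previous 12 months". The non-biologic comparator group is formed by "inclusion of patients with a prescription of SLE SOC and exclusion of those with a prescription of SLE SOC biologics in the previous 12 months". Neither section limits the rule by route or makes an exception for France.

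Section 10.9 acknowledges that French patients given IV drugs may be misclassified, but only for the start and end of standard of care and for SLE severity. The France standard-of-care cell of Table 7 says available, outpatient, apart from voclosporin and mepacrine, which a footnote describes as not marketed.

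**The concern.** The split shows whether the primary result depends on the type of comparator. That requires both comparator groups to be what their labels say. In France, absence of a biologic record does not mean absence of a biologic, because one of the two drugs that define the class is invisible when given by infusion.

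Three things follow for a French IV belimumab user who has some other recorded standard of care and no recorded rituximab or pen belimumab in the window:

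- as a comparator, the patient qualifies as non-biologic;
- as an anifrolumab starter, the patient is not removed from the biologic-free exposed arm;
- the patient is missing from the French biologic group, which shrinks to rituximab and pen belimumab users.

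The French non-biologic group then partly contains biologic users. If the two contrasts agree, a reader would take this as robustness to comparator type, although part of the agreement could come from misfiling. Propensity-score matching, which Section 10.9 offers as mitigation for uncaptured IV drugs, cannot recover an unrecorded drug that itself defines the group.

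**Working it through.** **1. Weight of France.** Table 8 gives average SLE patients per year of 1,122 (Denmark), 15,501 (France), 1,224 (Germany) and 2,944 (Spain), total 20,791.

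- 15,501 / 20,791 = 74.56%, which reproduces the French share in Table 13.
- 0.7456 × 3,195 = 2,382 and 0.7456 × 1,312 = 978, which reproduce its French sample sizes.
- Expected initiators (Table 8): 2,695 / 3,506 = 76.9% for malignancy and 1,005 / 1,435 = 70.0% for serious infection.

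**2. Who is misfiled in France when the 12-month rule is applied to what SNDS records.**

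| Treatment in previous 12 months (plus other recorded standard of care) | Recorded as biologic? | Group as comparator |
|---|---|---|
| IV rituximab | yes | biologic, correct |
| Pen belimumab | yes | biologic, correct |
| IV belimumab plus a recorded biologic | yes | biologic, correct |
| IV belimumab only | no | non-biologic, wrong |
| No biologic | no | non-biologic, correct |

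Only the fourth row is wrong. The same row is wrongly kept in the exposed arm.

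**3. Effect on the non-biologic HR (illustration; q, r, s and u are not in the protocol).** Let q be the share of French non-biologic comparators really on IV belimumab, and r their outcome rate relative to true non-biologic users. With only the comparator arm affected, observed HR ≈ true HR / (1 − q + q·r). For a true HR of 1.5:

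| q | r = 0.7 | r = 1 | r = 2 |
|---|---|---|---|
| 5% | 1.52 | 1.50 | 1.43 |
| 10% | 1.55 | 1.50 | 1.36 |
| 20% | 1.60 | 1.50 | 1.25 |
| 30% | 1.65 | 1.50 | 1.15 |

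The exposed arm has the same gap. If a share s of it had recent unrecorded IV belimumab with relative rate u, the observed HR ≈ true HR × (1 − s + s·u) / (1 − q + q·r). With s = q and u = r the two factors cancel. Neither sign nor size is therefore fixed.

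**4. Effect on the comparison of the two contrasts.** Let N and B be the non-biologic and biologic rates, and assume misfiled patients have rate B. The observed non-biologic rate is (1 − q)N + qB, so the difference from B is (1 − q)(B − N). At q = 10%, 90% of the true difference remains; at q = 30%, 70%. Under that assumption the error pulls towards agreement.

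**5. Plausible size of q.** Appendix 4.3 assumes that at the 2032 peak 40–50% of patients are on biologics, 40–50% of them on anifrolumab. Other biologics then cover 0.40 × 0.50 = 20% to 0.50 × 0.60 = 30% of patients.

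- High end (30% other, 50% none): q = 30% needs x / (x + 50) = 0.30, x = 21.4, or 21.4 / 30 = 71% of other-biologic use to be IV belimumab.
- Low end (20% other, 60% none): the maximum is 20 / 80 = 25%, so 30% cannot be reached.

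Enrolment closes in 2025 and 2028, before that peak, so q = 30% is an extreme value.

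**The case against.** The strongest reply has four parts.

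- **Country reporting and deferral.** Section 10.7 already promises results by country. Section 10.6 onward does not say that the split is pooled: Section 10.7.1.6 restricts meta-analysis to the primary objectives. Section 10.3 leaves source-specific definitions to local protocols and the SAP. This stands in part: it limits the importance of the French share, and a French label could be set in the SAP. But the protocol fixes a classification rule that its largest source cannot apply as written, and a separate French result would still carry the wrong labels. Section 10.7.1.7 attaches these analyses to the primary objectives, so a pooled version is not ruled out.
- **Magnitude.** The share and relative rate are assumed, and both arms have the gap. This stands; no figure for the bias can be claimed.
- **Dropping France.** This would leave 3,506 − 2,695 = 811 malignancy and 1,435 − 1,005 = 430 serious-infection initiators, before the further exclusion of recent biologic users. At HR 1.5, SD 0.2, 1:3 matching and the SLE rates, Table 10 gives power 0.358 at 500 and 0.511 at 1,000; Table 12 gives 0.569 at 500. This stands against replacing the French result.
- **Other sources.** Germany cannot see inpatient administration or identify drugs in visits paid as a diagnosis-related group. Table 26 notes that Spain's prior immunosuppressant history omits drugs given during hospitalisation. This also stands.

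Stronger readings are tempting. A reader might infer that IV biologics in general are misfiled; IV rituximab is captured, so they are not. A reader might see Table 7 as contradicting Section 10.4.1.2; its cell says outpatient and its exceptions are unmarketed drugs, so it is incomplete rather than contradictory. Because Section 10.4 says a biologic "with a similar administration route (belimumab IV infusion) was used as a proxy", a reader might infer that anifrolumab is also invisible in France; Section 10.4.1.2 instead rests its capture on expected high-cost listing.

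**Conclusion.** The point holds in a limited form. Applied as written, the 12-month rule misfiles French patients whose only biologic in the window is IV belimumab, in both the comparator and the exposed arm, in the source expected to supply 70.0% to 76.9% of initiators. Section 10.9 does not cover this consequence.

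The affected results are the biologic/non-biologic sensitivity analyses of objectives 1 to 4. The primary comparison pools all standard of care, so its arms are not defined by this class, and nothing here shows that it is invalid.

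The direction and size of the bias are unknown. The illustrative HRs rest on assumed values for the misfiled share and the relative rate and ignore the exposed arm; if the relative rate is 1, the non-biologic HR is unbiased. The pull towards agreement rests on the further assumption that misfiled patients share the biologic group's rate. What can be said firmly is that agreement between the two French contrasts is not, by itself, evidence of robustness to comparator type.

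**What to change.** - In Sections 10.2.2.2 and 10.7.1.7 and Table 5, define and label the French groups by captured products: 'rituximab or pen belimumab' and 'no captured biologic; IV belimumab not recorded'. Apply the second label to the French exposed arm as well.
- Keep the French result. Report any cross-country summary of the split both with and without France.
- State that agreement between the two French contrasts will not be read as robustness to comparator type.
- Add the limitation to Section 10.9, and note there the German and Spanish in-hospital gaps.
- Add a footnote on IV belimumab to the France standard-of-care cell of Table 7.

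The cost is wording in the protocol and SAP plus one additional summary. The result without France will be imprecise, as the power figures above show, and should be presented as such. The primary analysis and the sample size are unchanged.

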10.4.1.3 Germany: Statutory Health Insurance Providers Claims

In Germany, insurance claims from approximately 8-10 different statutory health insurance (SHI) providers are collected by Team Gesundheit. SHI is a requirement for individuals with a permanent place of residence in Germany, even for short-term stays. Since 2012, all individuals in Germany have a specific identifier which would not change throughout lifetime. SHI covers 89% of German population; data available through the Team Gesundheit represents 5-6% of the German population, representative in terms of age, gender and region. This data source has been used for different research purposes, including oncology [18, 36] and rheumatic diseases treated with biologic agents [102].

Data on medications cover prescriptions in primary care and community pharmacy dispensing. Data on medication use in inpatient setting are not available. Data on drugs administered in outpatient visits at the hospital are captured, unless the hospital visit is reimbursed as diagnosisrelated group (DRG). In that case it will not be possible to know which drug was administered as only one generic code will be available. Drug indication is not available since there is no active link between diagnosis and the prescribed therapy. Dose can be derived from the quantity prescribed and the period between prescription dates. Prescription and dispensation dates are available, but not for over-the-counter products and substances not reimbursed.

The database contains information from primary care and in- and outpatient hospital care. Data on physician visits, specialist code of the treating physician (e.g., gastroenterology), and hospitalisations are available. For inpatient stays, primary diagnoses and secondary diagnoses are available, primary diagnoses are a proxy for "cause of hospitalisation".

Diagnosis information is available and captured using the ICD-10 coding system with German modification (GM). Data on surgical and medical procedures are recorded using the GM of the ICD-10-PCS (ICD-10 Procedure Coding System) and the operation and procedure classification system (*Operationen und Prozedurenschlüssel* [OPS]). Due to the nature of the claims data, information on data that are not subject to reimbursement are not visible in the database. For

example, information on symptoms captured by ICD-10 coding would have little or no coverage as they are usually not subject to reimbursement.

Similarly, information on a conducted diagnostic test is only available if being subject to reimbursement. Test results are not available from the claims data. Sociodemographic information is partially available. However, data on lifestyle factors are not recorded.

SHI data in Germany are updated yearly. The estimated lag time (from the time data are recorded until available for research) is currently 15-16 months or more. At the time of feasibility assessment (June 2022) data for the period between January 2011 up to December 2020 were available; data from 2022 will be available in 2024.

Study-specific data

In Germany, market launch for anifrolumab occurred in March 2022 (Table 3). Anifrolumab is expected to be captured, since belimumab data are available through prescription or dispensation. Administration during hospital stay is not captured.

Data on SLE SOC exposure is considered available for most drugs since 2011, except for mepacrine which is no longer available in Germany. Data on prescribed outpatient therapy are available. Data on biologics are available through prescription data on German national drug code unique identifier (*Pharmazentralnummer* [PZN]) level and some OPS inpatient codes.

Data on malignancies (overall and sub-types) and serious infections (overall and sub-types) are available for inpatients and outpatients if coded trough ICD-10 GM. Date of death is available. Intravenous antimicrobials can be captured from the prescriptions and dispensations in outpatient visits.

Data on covariates are generally available (Table 26), except for vaccination (substance not captured), BMI (including weight or height), alcohol consumption and smoking. Procedures with radiation exposure may be available if procedure codes are registered.

